6.5. Baseline and Other Summaries and Analyses

6.5.1. Baseline Summaries

Descriptive summaries of baseline demographic and disease characteristics will be provided. For binary/categorical characteristics sample size and the number and percent with each level will be and presented. For continuous characteristics the sample size, mean, standard deviation, 95% CIs, minimum, maximum, median and 25th and 75th percentile values will be presented.

6.5.2. Study Conduct and Subject Disposition

The number entering, completing and discontinuing from each treatment period will be tabulated for each treatment period. Discontinuations will be further summarized by reasons for discontinuation.

6.5.3. Study Treatment Exposure

Descriptive statistics for compliance will be provided. The proportion of compliant subjects, defined as those having taken at least 80% of the expected doses over the entire treatment interval, will be tabulated.

6.5.4. Concomitant Medications and Non-Drug Treatments

Prior and concomitant medications will be coded using the WHO Drug dictionary. The numbers of subjects using concomitant medications will be categorized by drug category and preferred term, and presented for each treatment group.

Concomitant medications and non-study treatments will be summarized separately for each period.

6.6. Safety Summaries and Analyses

Safety data (demographics, vital signs, laboratory data, adverse events, demographics, primary diagnosis and duration, medical history, concomitant medications, treatment durations and discontinuations) will be analyzed in accordance with Pfizer Data Standards (PDS). CCI [REDACTED]

Safety analyses will be based on the Safety Analysis Population and will be tabulated separately for each study period and over all periods for etanercept. Specific tables to be included will be summarized in a separate document.

It should be recognized that most studies are not designed to reliably demonstrate a causal relationship between the use of a pharmaceutical product and an adverse event or a group of adverse events. Except for select events in unique situations, studies do not employ formal adjudication procedures for the purpose of event classification. As such, safety analysis is generally considered as an exploratory analysis and its purpose is to generate hypotheses for further investigation.

6.6.1. Adverse Events

The number and percentage of patients experiencing at least one adverse event will be summarized overall, and by body system and preferred term for each study period. In any given category, subjects will only be counted once. Adverse events will further be categorized and summarized by severity and study drug relationship, as well as those that cause withdrawal, result in a dose reduction or in concomitant therapy.

6.6.2. Laboratory Data

Continuous and binary laboratory data will be summarized following the approaches defined for those data types in [Section 6.2](#).

6.6.3. Vital Signs

Continuous and binary vital signs data will be summarized following the approaches defined for those data types in [Section 6.2](#).

7. INTERIM ANALYSES

7.1. Introduction

No interim analysis with the aim of stopping or modifying the trial in any way is planned. The study will not have a data monitoring committee.

7.2. Interim Analyses and Summaries

Descriptive analyses of Period 1 will be performed when all subject data for Period 1 is complete.

9. APPENDICES

Appendix 1. DATA DERIVATION DETAILS

Appendix 1.1. Calculation of NSAID Intake Total Score

The general formula for calculation of the NSAID intake total score is:
 (equivalent NSAID score) × (days of intake during period of interest) × (days per week) /
 (period of interest in days).

The equivalent NSAID score in this formula can be obtained from the table below. The table shows the doses of various commonly used NSAIDs that are considered equivalent to a 150 mg dose of diclofenac. A 150 mg daily would be used to achieve optimal symptomatic control of a patient with axial SpA. Diclofenac 150 mg is assigned a score of 100. The equivalent score for other NSAIDs can be determined based on their dose. A 20 mg dose of piroxicam, since it is equivalent to a 150 mg dose of diclofenac is also assigned a score of 100. A 1200 mg dose of ibuprofen would have a score of 50 (since it is half of the equivalent dose).

| NSAID | Dose (mg) comparable to 150 mg of diclofenac |
|----------------|--|
| Diclofenac | |
| Naproxen | 1000 |
| Aceclofenac | 400 |
| Celecoxib | 200 |
| Etodolac | 600 |
| Etoricoxib | 90 |
| Flurbiprofen | 200 |
| Ibuprofen | 2400 |
| Indometacin | 150 |
| Ketoprofen | 200 |
| Meloxicam | 15 |
| Nimesulide | 200 |
| Phenylbutazone | 400 |
| Piroxicam | 20 |
| Tenoxicam | 20 |

As an example, suppose a 12 week period from baseline through week 12 (84 days) is of interest. During this period, a subject took piroxicam 4 times a week at a dose of 20 mg for the first 8 weeks and then switched to ibuprofen 2 times a week at a dose of 1200 mg for the last 4 weeks. Based on the table, the equivalent score for 20 mg of piroxicam is $[100 \times 56 \times (4/7)]/84 = 38.1$, and the score for ibuprofen is $[50 \times 28 \times (2/7)]/84 = 4.8$.

The NSAID intake score for this subject for this 12 week period is $38.1 + 4.8 = 42.9$.

Notes:

Follow up based on NSAIDS identified in the study but not included in the table above:

Lornoxicam – assigned the same dose equivalence as Piroxicam in the table

Alternative names for known medications were mapped as follows (unknown/known):

| |
|---------------------------------------|
| Olfen Uno/diclofenac |
| Orudis Retard/ketoprofen |
| Orudis depot/ketoprofen injection |
| Orudis Retard/ketoprofen |
| Salsalate/disalcid |
| Surgam/tiaprofenic acid |
| Trosicam/meloxicam |
| Xefo Rapid/lornoxicam |
| Xefo rapid/loroxicam |
| diclofenac/dicolfenac |
| diclofenacum natricum/diclofenac |
| naproxen and esomeprazole/naproxyn |

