3.3. Other Endpoints

3.3.1. Non-steroidal Anti-Inflammatory Drug (NSAID) Usage

Any NSAIDs taken as background medications during the study will be identified along with start and stop dates, average daily dose (mg) and treatment frequency (days per week). Details regarding the calculation can be found in [Appendix 1.1](#). This intake score will be calculated for each study period.

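### The general NSAID intake formula in SAP Appendix 1.1 lacks a division by 7 and contradicts the worked example below it (minor; no listed efficacy analysis uses the score)

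*SAP*

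**What the plan says.** SAP 3.3.1, under Other Endpoints, has background NSAIDs recorded with start and stop dates, "average daily dose (mg) and treatment frequency (days per week"), and refers to Appendix 1.1 for the calculation. It adds: "This intake score will be calculated for each study period".

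Appendix 1.1 then gives two things:

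- **A general formula.** The numerator is "equivalent NSAID score) × (days of intake during period of interest) × (days per week"; the denominator is the "period of interest in days". No 7 appears in either.
- **A worked example.** It begins "suppose a 12 week period from baseline through week 12 (84 days) is of interest". The first drug is described in these words: "a subject took piroxicam 4 times a week at a dose of 20 mg for the first 8 weeks". The second drug, covering the remaining 28 days, is ibuprofen 1200 mg on two days of each week. The frequencies enter as 4/7 and 2/7, the two parts come to 38.1 and 4.8, and the total is 42.9.

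The appendix also anchors the scale. Diclofenac 150 mg, described as the daily amount for optimal symptom control, scores 100. So does piroxicam 20 mg, and ibuprofen 1200 mg scores 50.

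**The concern.** The rule and its illustration give different answers for the same subject. SAP 3.3.1 collects frequency as a count of days per week, so a programmer who puts the collected variable into the printed formula multiplies by a number from 1 to 7 where the example multiplies by a fraction of at most 1. Nothing elsewhere in the SAP or protocol supplies the missing division.

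What is at stake is the readability of a descriptive exposure measure. NSAID is the background treatment kept on when etanercept is withdrawn. Protocol 5.8 rules out dose increases in Periods 2 and 3 but allows reductions for adverse events, and it lets a subject who does not tolerate the lower dose stay in the study. NSAID exposure can therefore vary between subjects while flare is being observed, and this score is the SAP's quantitative summary of it. A tabulated value of 300 or 700 could not be read against an anchor of 100 for a full daily dose.

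**Working it through.** **Inputs, all from SAP Appendix 1.1**

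- Period of interest: 84 days.
- Piroxicam 20 mg: score 100, 4 days per week, 8 weeks = 56 calendar days.
- Ibuprofen 1200 mg: score 50, 2 days per week, 4 weeks = 28 calendar days.

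**Step 1. Reproduce the SAP's figure.** The example uses score × days × (days per week / 7) / period.

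- Piroxicam: 100 × 56 × (4/7) / 84 = 38.10
- Ibuprofen: 50 × 28 × (2/7) / 84 = 4.76
- Total: 42.86, which rounds to the stated 42.9.

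**Step 2. Apply the general formula as printed.** This is score × days × days per week / period.

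- Piroxicam: 100 × 56 × 4 / 84 = 266.67
- Ibuprofen: 50 × 28 × 2 / 84 = 33.33
- Total: 300.0

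The ratio is 300.0 / 42.86 = 7.00, and it is 7.00 for each drug separately.

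**Step 3. Check against the anchor.** Take a full equivalent dose every day for 84 days.

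- As printed: 100 × 84 × 7 / 84 = 700
- With the division by 7: 100 × 84 × (7/7) / 84 = 100

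Only the second agrees with a score of 100 for diclofenac 150 mg daily, so the formula line is the part to correct.

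**Step 4. Try another reading of days of intake.** Suppose it means days on which a dose was actually taken: 56 × 4/7 = 32 and 28 × 2/7 = 8.

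| Version | Piroxicam | Ibuprofen | Total |
|---|---|---|---|
| Formula as printed | 100 × 32 × 4 / 84 = 152.4 | 50 × 8 × 2 / 84 = 9.5 | 161.9 |
| With the division by 7 | 100 × 32 × (4/7) / 84 = 21.8 | 50 × 8 × (2/7) / 84 = 1.4 | 23.1 |
| No frequency term | 100 × 32 / 84 = 38.1 | 50 × 8 / 84 = 4.8 | 42.9 |

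This reading does not rescue the printed formula. It also shows that adding the 7 is not enough by itself: under dosing days, the corrected formula counts frequency twice and gives 23.1. The term has to be defined as the example uses it.

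**The case against.** The strongest reply is that the example settles the intent. It substitutes every term for two drugs directly under the formula, and the anchor of 100 points the same way. A programmer who tests code against it would see the factor of 7 at once, and 700 for ordinary daily use would look implausible. On this view the formula is loosely worded and its own example corrects it. That largely stands, and it is the main reason for a low grade. It does not remove the contradiction: the formula is presented as the general rule, SAP 3.3.1 gives the frequency as a count, and a derivation specification should not leave the programmer to choose between rule and illustration.

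The second reply is that little depends on the score. This also stands. It is not in the primary flare analysis or the Cox covariates of SAP 6.1.1.1, where prior NSAID response is a different variable. It is not among the endpoints named in SAP 6.2 or the subgroups in SAP 6.4. A uniform factor of 7 would also leave rankings and ratios between subjects or periods unchanged; only the absolute level would be wrong.

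A reader might infer that the reported scores are wrong for every subject. The documents do not show that, because nothing in them says which line the code follows. The SAP's version history records that Appendix 1.1 was revisited in version 2 to classify further NSAIDs. That shows the appendix was in use, but it is not evidence either way about the code. A reader might also take the score to be bounded at 100. The appendix fixes 100 as an anchor and states no upper limit, so a dose above the equivalent would score more.

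**Conclusion.** The inconsistency is real and lies in the formula line. As printed, the formula gives 300.0 where the SAP's example gives 42.9, and 700 where the anchor implies 100. The factor is exactly 7 provided that days of intake are calendar days on the drug, as the example's 56 and 28 are. It is not explained by text lost in extraction, since the formula reads continuously and the fractions in the example are intact.

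The consequence is conditional and confined to one descriptive endpoint: scores are inflated only if the program was written from the formula and not from the example. It would be going too far to conclude that the flare estimate or the comparison with B1801031 is affected, because neither uses this score. Severity: minor.

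**What to change.** Restate the formula in SAP Appendix 1.1 as the sum over NSAIDs of

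(equivalent NSAID score) × (days of intake) × (days per week / 7) / (period of interest in days).

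Define days of intake as calendar days from start to stop of the drug within the period, and note that these are the 56 and 28 of the example. Then confirm that the derivation program returns 42.9 for the example subject.

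The cost is a short text correction and one program check. No design feature, data collection or listed efficacy analysis changes.

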Appendix 1.2. Criteria for Potentially Clinically Important (PCI) Laboratory Values

Laboratory test results that were Grade 3 or Grade 4 according to the National Cancer Institute Common Terminology Criteria for Adverse Events) will be considered Potentially Clinically Important (PCI).

| Laboratory Test | Grade | Criteria |
|----------------------|-------|---|
| Neutrophils | 1 | 1.5 <= value < 2.0 |
| | 2 | 1.0 <= value < 1.5 |
| | 3 | 0.5 <= value < 1.0 |
| | 4 | value < 0.5 |
| Hemoglobin | 1 | 100 <= value < Lower range |
| | 2 | 80 <= value < 100 |
| | 3 | 65 <= value < 80 |
| | 4 | value < 65 |
| Lymphocytes | 0 | value >= 1.5 |
| | 1 | 1.5 > value >= 1.0 |
| | 2 | 1.0 > value >= 0.5 |
| | 3 | 0.5 > value |
| Platelets | 0 | value >= Lower range |
| | 1 | Lower range > value >= 75.0 |
| | 2 | 75.0 > value >= 50.0 |
| | 3 | 50.0 > value >= 25.0 |
| | 4 | 25.0 > value |
| White Blood Count | 0 | value >= 4.0 |
| | 1 | 4.0 > value >= 3.0 |
| | 2 | 3.0 > value >= 2.0 |
| | 3 | 2.0 > value >= 1.0 |
| | 4 | 1.0 > value |
| Alkaline Phosphatase | 0 | value <= 1.0*Upper range |
| | 1 | 1.0*Upper range < value <= 2.5*Upper range |
| | 2 | 2.5*Upper range < value <= 5.0*Upper range |
| | 3 | 5.0*Upper range < value <= 20.0*Upper range |
| | 4 | 20.0*Upper range < value |
| SGOT/AST | 0 | value <= 1.0*Upper range |
| | 1 | 1.0*Upper range < value <= 3.0*Upper range |
| | 2 | 3.0*Upper range < value <= 5.0*Upper range |
| | 3 | 5.0*Upper range < value <= 20.0*Upper range |
| | 4 | 20.0*Upper range < value |
| SGPT/ALT | 0 | value <= 1.0*Upper range |
| | 1 | 1.0*Upper range < value <= 3.0*Upper range |
| | 2 | 3.0*Upper range < value <= 5.0*Upper range |
| | 3 | 5.0*Upper range < value <= 20.0*Upper range |

| Laboratory Test | Grade | Criteria |
|--------------------------|-------|---|
| | 4 | 20.0*Upper range < value |
| Total bilirubin | 1 | value <= 1.0*Upper range |
| | 2 | 1.0*Upper range < value <= 1.5*Upper range |
| | 3 | 1.5*Upper range < value <= 3.0*Upper range |
| | 4 | 3.0*Upper range < value |
| Creatinine | 0 | value <= 1.0*Upper range |
| | 1 | 1.0*Upper range < value <= 1.5*Upper range |
| | 2 | 1.5*Upper range < value <= 3.0*Upper range |
| | 3 | 3.0*Upper range < value <= 6.0*Upper range |
| | 4 | 6.0*Upper range < value |
| Albumin | 0 | value > 35.0 (=LLN) |
| | 1 | 35.0 >= value >= 30 |
| | 2 | 30.0 > value >= 20.0 |
| | 3 | 20.0 > value |
| | 4 | (no values given) |
| Urea | 0 | value <= 1.5*Upper range |
| | 1 | 1.5*Upper range < value <= 2.0*Upper range |
| | 2 | 2.0*Upper range < value <= 3.0*Upper range |
| | 3 | 3.0*Upper range < value <= 4.0*Upper range |
| | 4 | 4.0*Upper range < value |
| Potassium - high and low | 0 | 3.4 (=LLN) < value < 5.0 (=ULN) |
| | 1 | 5.0 <= value <= 5.5 or <3.4 >= value >= 3.0 |
| | 2 | 5.5 < value <= 6.0 or <3.4 >= value >= 3.0 |
| | 3 | 6.0 < value <= 7.0 or 3.0 > value >= 2.5 |
| | 4 | value > 7.0 or value < 2.5 |
| Sodium - high & low | 0 | 134 (=LLN) < value < 146 (=ULN) |
| | 1 | 146 <= value <= 150 or 140 >= value >= 130 |
| | 2 | 150 < value <= 155 or (no values given) |
| | 3 | 155 < value <= 160 or 130 > value >= 120 |
| | 4 | value > 160 or value < 120 |

Appendix 1.3. Criteria for Potentially Clinically Important (pci) Vital Signs Values

| Test | Definition |
|----------------------------------|---|
| Sitting Pulse Rate | Increase from baseline ≥ 15 beats/min and ≥ 120 beats/min |
| | Decrease from Baseline ≥ 15 beats/min and ≤ 50 beats/min |
| Sitting Systolic Blood Pressure | Increase from baseline ≥ 20 mm Hg and ≥ 160 mm Hg |
| | Decrease from baseline ≥ 20 mm Hg and ≤ 90 mm Hg |
| Sitting Diastolic Blood Pressure | Increase from baseline ≥ 15 mm Hg and ≥ 90 mm Hg |
| | Decrease from baseline ≥ 15 mm Hg and ≤ 60 mm Hg |
| Weight | Increase from baseline $\geq 15\%$ and ≥ 25 lbs (11.36 Kg) |
| | Decrease from baseline $\geq 15\%$ and ≤ 25 lbs (11.36 Kg) |

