  22. Pregnant female subjects; breastfeeding female subjects; male subjects with partners currently pregnant; male subjects able to father children and female subjects of childbearing potential who are unwilling or unable to use a highly effective method of contraception as outlined in this protocol for the duration of the study and for at least 28 days after the last dose of investigational product or longer based upon the compound's half-life characteristics.

23. Subject has an abnormal hematology or blood chemistry profile during the screening period. Refer to [Section 6.8](#) for management of exclusionary lab values at baseline.

- White blood cell (WBC) count  $<3.5 \times 10^9/L$ ;
- Hemoglobin level  $<8.5 \text{ g/L}$  or  $<5.3 \text{ mmol/L}$ ;
- Hematocrit  $<27\%$ ;
- Platelet count  $<125 \times 10^9/L$ ;
- Serum creatinine level  $>175 \text{ } \mu\text{mol/L}$  ( $>1.98 \text{ mg/dL}$ );
- AST or ALT level  $>2$  times the laboratory's ULN.

24. Other severe acute or chronic medical or psychiatric condition or laboratory abnormality that may increase the risk associated with study participation or investigational product administration or may interfere with the interpretation of study results and, in the judgment of the investigator, would make the subject inappropriate for entry into this study. Subject has any clinically relevant concurrent medical conditions, including;

- Known history or presence of acute or chronic hepatitis B or hepatitis C or human immunodeficiency virus (HIV) infection; (If required by Health Authorities, an HIV test must be performed at a local lab during screening. Results of this test will be used to determine eligibility).
- Uncompensated congestive heart failure, or class III or IV heart failure defined by the New York Heart Association classification;
- Uncontrolled hypertension (defined as screening systolic blood pressure  $>160 \text{ mm Hg}$  or screening diastolic blood pressure  $>100 \text{ mm Hg}$ );
- Myocardial infarction within 12 months before the screening visit;
- Coronary artery by-pass graft (CABG) or percutaneous transluminal coronary angioplasty (PTCA) within 12 months before the first dose visit;
- Unstable angina pectoris within 6 months before the screening visit;
- Severe pulmonary disease requiring recurrent hospitalization or supplemental oxygen;
- Presence or history of confirmed blood dyscrasias;

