### **6.8. Subject Withdrawal**

The sponsor's Clinical team must be consulted as soon as possible if any of the following occur during the active treatment period (Period 1 or Period 3) to determine whether the subject should continue taking the investigational product:

- Any infection requiring parenteral (IV, IM) anti-infective agents but not meeting criteria for serious infection (see below).
- The sponsor's Clinical team must be notified as soon as possible if a subject is planning to undergo or has undergone any surgical procedure. It is recommended that investigational product be withheld surrounding most surgical procedures.
  - For most planned surgeries, investigational product should be withheld for a period of time prior to the procedure; the specific duration should be determined by the clinical judgment of the investigator;
  - Investigational product should be withheld following most surgeries. The investigational product can be reintroduced once the investigator judges the risk for post-operative infection to be low;
  - If it is clinically judged that more than two consecutive weekly doses of investigational product should be withheld, then the subject must be withdrawn from the study.
- Lack of compliance with the protocol, including protocol required schedule of study visits and/or lack of procedures.

Subjects **MUST** be withdrawn from investigational product if any of the following occurs:

- If baseline lab value is confirmed to meet Exclusion criteria, the subject must be discontinued. Confirmation of the value should be performed prior to the Week 4 visit.
- Pregnancy.
- Grade 3 or 4 systemic toxicity or a SAE thought to be related to investigational product and not alleviated by symptomatic treatment after cessation of investigational product use of up to two doses or Grade 3 or 4 systemic toxicity that recurs after resumption of investigational product use (see [Appendix 5](#)).

- Receipt of any live (attenuated) vaccines.
- Subjects with clinical signs and symptoms suggestive of active tuberculosis should have investigational product withheld until a diagnosis can be confirmed. If diagnosis or tuberculosis is confirmed, investigational product must be discontinued.
- Suspected sepsis.
- Any serious infection (defined as an infection meeting any SAE criteria).
- Confirmed blood dyscrasia or a demyelinating disorder (such as multiple sclerosis or optic neuritis).

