### **8.6.2. Potential Cases of Drug-Induced Liver Injury**

Abnormal values in AST and/or ALT levels concurrent with abnormal elevations in total bilirubin level that meet the criteria outlined below in the absence of other causes of liver injury are considered potential cases of drug-induced liver injury (potential Hy's law cases) and should always be considered important medical events.

The threshold of laboratory abnormalities for a potential case of drug-induced liver injury depends on the subject's individual baseline values and underlying conditions. Subjects who present with the following laboratory abnormalities should be evaluated further to definitively determine the etiology of the abnormal laboratory values:

- Subjects with AST or ALT and total bilirubin baseline values within the normal range who subsequently present with AST or ALT values  $\geq 3$  times the upper limit of normal ( $\times$  ULN) concurrent with a total bilirubin value  $\geq 2 \times$  ULN with no evidence of hemolysis and an alkaline phosphatase value  $\leq 2 \times$  ULN or not available;
- For subjects with preexisting ALT **OR** AST **OR** total bilirubin values above the ULN, the following threshold values should be used in the definition mentioned above:
  - For subjects with preexisting AST or ALT baseline values above the normal range: AST or ALT values  $\geq 2$  times the baseline values and  $\geq 3 \times$  ULN, or  $\geq 8 \times$  ULN (whichever is smaller).

Concurrent with

- For subjects with preexisting values of total bilirubin above the normal range: Total bilirubin level increased from baseline by an amount of at least  $1 \times$  ULN **or** if the value reaches  $\geq 3 \times$  ULN (whichever is smaller).

The subject should return to the investigational site and be evaluated as soon as possible, preferably within 48 hours from awareness of the abnormal results. This evaluation should include laboratory tests, detailed history, and physical assessment.

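### Three safety limits are wrong as written: the weight-loss flag caps the loss at 25 lb, bilirubin grades sit one step too high, and the two hemoglobin exclusion limits differ tenfold

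*SAP*

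**What the plan says.** **Weight (SAP Appendix 1.3).** The increase row asks for a gain of at least 15% and at least 25 lb. The decrease row asks for a loss of at least 15%, joined by *and* to "≤ 25 lbs (11.36 Kg"). In the pulse and blood pressure rows of the same table, the second limit is an absolute level, for example a systolic fall of at least 20 mm Hg to a reading of 90 mm Hg or lower.

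**Bilirubin (SAP Appendix 1.2).** The appendix defines PCI by "Laboratory test results that were Grade 3 or Grade 4 according to the National Cancer Institute" criteria. The lowest bilirubin row is "Total bilirubin | 1 | value <= 1.0*Upper range". The later rows put values above 1.0 and up to 1.5 times the upper range in Grade 2, above 1.5 and up to 3.0 times in Grade 3, and anything higher in Grade 4. The creatinine block begins "Creatinine | 0 | value <= 1.0*Upper range" and has the cut-points 1.0, 1.5 and 3.0, plus a further cut at 6.0. Alkaline phosphatase, AST and ALT also give normal values Grade 0.

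**Hemoglobin (Protocol 4.4, criterion 23).** The exclusion limit is given as below 8.5 g/L or below 5.3 mmol/L. Protocol 6.8 extends the exclusion limits to baseline results: "If baseline lab value is confirmed to meet Exclusion criteria, the subject must be discontinued". The SAP's own hemoglobin grading has Grade 2 at "80 <= value < 100", Grade 3 from 65 to below 80, and Grade 4 below 65.

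**The concern.** A flag for important weight loss should become more likely as the loss grows. Here a larger loss can remove the flag. The probable cause is that the reversed sign, which is right for an absolute level in the pulse and blood pressure rows, was carried into a row where the second limit is a change.

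For bilirubin, a normal result carries an abnormal grade, and the whole scale is shifted up by one. Because PCI is tied to Grades 3 and 4, the shift lowers the flagging threshold. For hemoglobin, one criterion contains two limits that cannot both be meant.

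Estimating safety and tolerability is a stated secondary objective (Protocol 2.1.2). Code written to the SAP as it stands would give a weight-loss flag that ignores the largest losses and a PCI count for bilirubin that is too high. A site that applied only the g/L figure for hemoglobin would in practice exclude nobody.

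**Working it through.** **Weight.** Inputs from SAP Appendix 1.3: 15% and 25 lb, given as 11.36 kg. The conversion reproduces as 25/2.2 = 11.36.

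*Reading 1: 25 lb is the size of the change.* With baseline weight W, the flag needs 0.15 × W ≤ loss ≤ 11.36 kg. This window is empty once 0.15 × W > 11.36, that is, for W > 11.36/0.15 = 75.7 kg. The table compares the rule as written with two corrections: *mirror* (at least 15% and at least 25 lb, so loss ≥ max(0.15 × W, 11.36)) and *15% only*.

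| Baseline | As written | Mirror | 15% only |
|---|---|---|---|
| 50 kg | 7.5 to 11.36 kg (15 to 22.7%) | ≥ 11.36 kg (22.7%) | ≥ 7.5 kg |
| 60 kg | 9.0 to 11.36 kg (15 to 18.9%) | ≥ 11.36 kg (18.9%) | ≥ 9.0 kg |
| 70 kg | 10.5 to 11.36 kg (15 to 16.2%) | ≥ 11.36 kg (16.2%) | ≥ 10.5 kg |
| 90 kg | none (13.5 > 11.36) | ≥ 13.5 kg (15%) | ≥ 13.5 kg |

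A 90 kg subject who loses 20 kg (20/90 = 22.2%) is not flagged as written, but is flagged under both corrections. A 55 kg subject who loses 10 kg (10/55 = 18.2%) is flagged as written and under 15% only, but not under the mirror rule, which at 55 kg needs 11.36/55 = 20.7%.

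*Reading 2: 25 lb is an absolute weight.* The subject would have to weigh 11.36 kg or less. All subjects are adults (Protocol 4.1, criterion 10), so the flag never fires.

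Reading 1 is the likelier one. As an absolute weight, the 25 lb in the increase row would hold for every adult and would do nothing. The row fails on both readings.

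**Bilirubin.** The same multiples of the upper range, graded with each set of rows in SAP Appendix 1.2:

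| Multiple of upper range | Bilirubin rows | Creatinine rows |
|---|---|---|
| 0.8 | 1 | 0 |
| 1.2 | 2 | 1 |
| 2.0 | 3 (PCI) | 2 |
| 3.5 | 4 (PCI) | 3 (PCI) |

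Up to 6 times the upper range, bilirubin sits exactly one grade above creatinine. PCI starts above 1.5 times as written and above 3.0 times once the rows are renumbered from 0. The Grade 1 label on normal values has no PCI effect in itself. Values between 1.5 and 2.0 times would be PCI although they lie below the bilirubin level of 2 times the upper limit that Protocol 8.6.2 uses for subjects with normal baseline values.

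**Hemoglobin.** The documents give no conversion factor. Assume 16.0 to 16.2 g per mmol.

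- 5.3 mmol/L is 5.3 × 16.0 = 84.8 to 5.3 × 16.2 = 85.9 g/L.
- 8.5 g/L is 8.5/16.2 = 0.52 to 8.5/16.0 = 0.53 mmol/L.
- The ratio of the two limits is 84.8/8.5 = 9.98 to 85.9/8.5 = 10.1.
- 8.5 g/dL is 85 g/L, or 85/16.2 = 5.25 to 85/16.0 = 5.31 mmol/L, in line with the stated 5.3.

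No factor is needed to see the problem. The SAP's hemoglobin grades have the size of g/L values. On that scale 8.5 lies far below the Grade 4 limit of 65, while 85 falls in Grade 2.

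The hematocrit limit of 27% in criterion 23 covers the gap only in part. A subject with hemoglobin below 8.5 g/dL passes it if the mean corpuscular hemoglobin concentration is below 8.5/0.27 = 31.5 g/dL.

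**The case against.** The strongest reply is that little depends on these limits.

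- **Reach.** No decision rule shown uses a PCI flag. SAP 6.6 treats safety analysis as exploratory and leaves the list of tables to a separate document. The legible SAP text outside the appendices does not refer to Appendix 1.2 or 1.3, although part of SAP 6.6 is redacted. This stands, so the effect is claimed for the flag definitions and one eligibility limit only. Large weight losses would still appear in listings (Protocol 9.3) and as the minimum change from baseline (SAP 6.2.2 and 6.6.3).
- **Bilirubin errs on the safe side.** Extra values are flagged and none is missed. The liver rule in Protocol 8.6.2, under which qualifying enzyme and bilirubin elevations "are considered potential cases of drug-induced liver injury", is separate and unaffected. Both points are right. It can also be said that the NCI criteria govern rather than the table, and that shared cut-points do not prove shared grades, since urea is graded differently. But a normal value at Grade 1 is wrong beside alkaline phosphatase, AST, ALT and creatinine. If the NCI text does govern, a table that departs from it still needs correcting.
- **Hemoglobin is covered by the *or*.** A subject below 5.3 mmol/L is excluded whatever the g/L figure says. Hematocrit and criterion 24, which covers a "laboratory abnormality that may increase the risk associated with study participation", add further protection. This largely stands. The error matters only where a site works from the mass figure alone.
- **The weight remedy is a choice.** The two corrections give different results in lighter subjects, and choosing between them is a clinical matter. That is so, but either one is better than a rule that drops the largest losses.

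**Conclusion.** All three limits are wrong as written, and the effect is confined to safety reporting and one eligibility limit. The primary flare estimate is not affected.

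The weight flag is the most serious of the three because it is the only one that misses important events: it cannot fire above 75.7 kg, and at 70 kg it covers only losses of 10.5 to 11.36 kg. The SAP's own weight subgroups split at 70 kg (SAP 6.4), so the affected range is not remote. Bilirubin is over-flagged between 1.5 and 3.0 times the upper range. The hemoglobin limits differ about tenfold, with small practical effect if sites apply both.

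The weight result holds on either reading of 25 lb. The bilirubin result rests on comparison within the SAP table, not on the NCI criteria, which were not available. The hemoglobin result rests on the assumed 16.0 to 16.2 g per mmol and is supported by the SAP's own grading scale.

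**What to change.** 1. **SAP Appendix 1.3.** Preferably drop the 25 lb condition for decreases, so that every loss of at least 15% is flagged. The alternative is at least 15% and at least 25 lb, mirroring the increase row. The sponsor would then accept that losses of 15% or more but under 25 lb, in subjects below 75.7 kg, are not flagged. If 25 lb is kept in either row, state that it is the size of the change.
2. **SAP Appendix 1.2.** Renumber the bilirubin rows from 0, with values above 3.0 times the upper range as Grade 3 or higher, or add a Grade 4 cut-point taken from the cited NCI criteria. PCI starts above 3.0 times either way.
3. **Protocol 4.4, criterion 23.** Change the mass limit to 8.5 g/dL (85 g/L), which agrees with 5.3 mmol/L.

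The cost is two appendix edits and one unit correction, with no new data. Only the weight and bilirubin PCI flags change in the outputs. The hemoglobin correction alters eligibility text, so it is a protocol amendment that needs ethics approval under Protocol 12.1. It can be made with the next amendment.
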